5.1 Screening and eligibility

All admitted patients were screened at admission by nursing staff for eligibility to use a standardized tablet and the associated MyChart Bedside application based on the following protocol, developed by OSUWMC:

1. Patients must have been admitted to a hospital in the OSUWMC system where MyChart Bedside has been deployed.
2. Patients must have been capable of accepting the tablet terms of service.
3. Patients must not have had an excluded status, which were:
 - a. less than 18 years old;
 - b. legally blind;
 - c. cannot speak and/or read English;
 - d. involuntarily confined or detained; or,
 - e. be considered as having a diminished decision-making capacity.

Nursing staff used their judgement in terms of whether a patient may have had an additional reason for exclusion and documented those reasons in the EHR. Acceptable reasons for exclusion included that the patient declined to use a tablet or the patient was not coherent at the time the nursing staff was rounding for the purpose of providing tablets. Patients were provided Android tablets by the medical center for use during their stay. The provisioning process defined the patient population and was outside of the scope of the study.

5.1.1 Inclusion criteria

Study inclusion criteria were as follows:

1. patient accepted tablet and use of MyChart Bedside;
2. patient was available in their room; and,
3. patient was capable of informed consent.

Only patients who were provisioned with MyChart Bedside were included in the study.

5.1.2 Exclusion criteria

Study exclusion criteria were as follows:

1. the patient was less than 18 years of age.

The inclusion criteria, by design, means that family and proxy users were excluded from the study.

5.2 Recruitment

The AMC Epic Clarity tables were used to develop a fully identified custom Census Report which provided information on all patients who met the inclusion criteria present in the hospital at midnight of each day. The research team integrated this report with the study database to create a daily list of individuals that had consented, refused, not been provided a tablet, or were eligible for being visited by a TN during TN rounding. This information was used to set up a rounding schedule to visit the rooms of these patients to follow up about study participation as follows:

1. In cases where a patient had not been provisioned and there were no clinical notes detailing a rationale for the withholding of access, members of the research team would approach the nursing team and ask them to make a formal determination about the appropriateness of the tablet for the patient.
2. In cases where a patient was provisioned, the study team would put the patient on the rounding schedule and attempt to recruit them to the study.

5.2.1 Study enrollment, participation, and remuneration

Eligible identified patients were invited to participate in the study via a link in MyChart Bedside which presented an electronic combined HIPAA authorization and consent form approved by the AMC's Institutional Review Board (IRB) for patients to sign to authorize extraction of identified clinical data. Study staff approached eligible patients to identify their interest in participation. Interested patients were guided to the tab within MyChart Bedside that explained that participation included the following tasks and consent:

1. a survey to be taken immediately upon completing consent (the Admission survey);
2. two surveys that would be taken by phone or via an emailed link;
 - a. The 15-day Post-discharge survey
 - b. The 6-month Post-discharge survey
3. additionally, patients were notified that they may be contacted for up to two telephone interviews: within 21 days of discharge and at approximately 6 months post-discharge. Not all individuals would be invited to participate in these interviews;
4. consent to share their clinical data, including the log files associated with their use of patient portals.

Upon completion of each survey, participants had the option to enter contact information on a separate page for a raffle of a \$100 gift card and for future follow-up for additional surveys and interviews. One gift card was raffled off each week throughout data collection.

Participants were provided the option to request a paper combined HIPAA authorization and consent form to sign, delivered by a study team member. Participants received an electronic copy of the signed combined HIPAA authorization and consent form or a paper version from a study team member within 24 hours. If the patient had been discharged, a paper version was mailed to the address on file.

5.3 Study withdrawal

All data collected during the period as study participants was included in the analysis. Individuals who chose to withdraw were, in effect, refusing to contribute further data, including the following:

1. Patients who removed themselves from the study prior to discharge in the admission in which they are enrolled had no data about them included in the study.
2. Patients who removed themselves from the study after discharge in the admission in which they are enrolled had the Admission survey data and MyChart Bedside use data about them included in the study, but depending on when they withdrew, may not have any data about them included as part of either of the Post-discharge surveys.
3. Patients who were not reachable after discharge for the 15-day Post-discharge survey were not considered lost to follow-up, and contact was attempted for the 6-month Post-discharge survey.

5.4 Baseline patient characteristics

Baseline characteristics were summarized, including age (median), gender (male, female percentages), race (White, Black, Other percentages), length of stay (days), and the Charlson comorbidity index (median, treated as a continuous score). Baseline characteristics were compared using analysis of variance (ANOVA) or t-tests, as appropriate, to examine equivalence between the four study arms.

Section 6: Data management

6.1 Data sources

Data for this study was merged from two sources—one delivered from surveys promulgated by Qualtrics, a cloud-based survey system, and the other from the OSUWMC Epic Clarity tables. Data was kept in separate tables in accordance with the study data model.

6.2 Data model

Five tables were used in the data model used for this study. Figure 2 illustrates the entity data diagram for each table in the data model and their relationship.

Data Table 1: Demographic Data	Data Table 2: Survey & Intervention Data	Data Table 3: Encounter Data	Data Table 4: Inpatient Portal Use Data	Data Table 5: Outpatient Portal Use Data

Record Identifier: ParticipantID
 
Provenance: Epic Clarity
 
Description: This dataset contains demographic information about each study participant.
	
Record Identifier: ParticipantID
 
Provenance: Qualtrics
 
Description: This dataset contains survey responses for the three study surveys as well as data about the intervention.
	
Record Identifier: ParticipantID EncounterID
 
Provenance: Epic Clarity
 
Description: This dataset contains information about each study participant's inpatient hospital encounter at an AMC facility.
	
Record Identifier: ParticipantID EncounterID
 
Provenance: Epic Clarity
 
Description: This dataset contains processed summaries of MyChart Bedside use at the session level for study participants.
	
Record Identifier: ParticipantID
 
Provenance: Epic Clarity
 
Description: This dataset contains processed summaries of MyChart outpatient portal use at the session level for study participants.

Figure 2. Entity data diagram.

Data Tables 1 and 2 provided data related to the participant. Intervention data was written into Qualtrics records from the EHR via a passthrough using a secure application programming interface (API). Data Tables 3 and 4 provided data about the patient's encounter history during the study period as well as their use of the inpatient portal for each visit. Data Table 5 provided data about the use of the outpatient portal, which therefore meant it was not related to a specific encounter. Where possible, the original data in the associated Epic Clarity tables were delivered to the research team, including the Admission/Discharge/Transfer (ADT) table. This approach was used to ensure that joins were completed by the research team as opposed to an intermediate data broker and ensure data quality.

6.3 Data processing

As noted in Section 6.2, data from the original Epic Clarity tables were provided to the research team. This process was deemed necessary, as quality testing of the data found a number of join errors that created issues when using the study and EHR

derived data. We detailed ten specific data quality issues that were found and resolved in the data quality assurance testing.

6.3.1 Multiple MRNs

MRNs were used as primary identifiers by both the hospital and in the context of the study. Moreover, MRNs were used throughout data processing to associate data with a unique patient. Typically, each unique patient had a single, unique MRN. In rare cases, for instance when a patient presented in the emergency room and was unable to provide identification, a patient may have been temporarily issued an MRN. While hospital records are adjusted to ensure a single, unique MRN at a later time, data was written to the log files with the temporary MRN. Patients with multiple MRNs were identified, along with their duplicate MRNs, and the identifiers were recoded to a “primary” MRN in the processed data.

6.3.2 Combining hospital encounters

In preliminary data processing, it was discovered that the ADT report contained both overlapping admissions as well as two separate admissions within close time proximity. These scenarios commonly occurred when an individual moved facilities for diagnosis and treatment; for instance, in the case of an individual in the general hospital moving to the heart hospital for testing. To resolve these issues, data analysts merged admissions within 4 hours of each other, as well as overlapping admissions, and considered them a single admission. Data quality tests found that approximately 9% of discharge-subsequent admission and overlaps were resolved by this threshold. In cases where a discharge was recorded and a subsequent admission was recorded more than four hours later, that admission was deemed to be a new, separate admission.

6.3.3 Matching admission surveys to a patient encounter

Both the MRN and the date and time of the start of the Admission survey was used to match an Admission survey to a specific patient encounter in the ADT table. However, Admission surveys were collected using two modalities—electronic and paper—the latter of which did not produce an electronic timestamp for survey start. In the first case, electronic data capture via the Qualtrics-hosted survey, MRN, and survey start/stop times were written to Data Table 2, however in cases where paper surveys were used, no such recording of start/ stop time was automatically recorded. In this latter case, the date and estimated time the survey was delivered was recorded in a separate administrative data system that included study team notes, which was merged into Data Table 2 after study completion. Given that dates, but not time, were used for merging, there was high confidence in this merging approach. Subsequent data checks provided quality assurance of this approach.

6.3.4 Merging use with encounters

There was no existing unique key to match MyChart Bedside use to hospital encounter data. To merge inpatient encounters with MyChart Bedside usage data, the merged encounter data discussed in 6.3.2 was used to establish admission and discharge dates and times. In these cases, the timestamp on the MyChart Bedside audit files was matched and used to link a user action to a specific encounter. Some user actions, approximately 1.5% of the raw MyChart Bedside log files, fell outside the encounter periods defined using the ADT record. Any actions that occurred outside an encounter period were dropped from further analyses.

6.3.5 MyChart Bedside user actions

MyChart Bedside log file data included 58 total actions that a user could perform. These actions could be classified into two categories: active and passive actions. Active actions were user initiated, required user engagement, and had exclusive and reliable representation in the log file across the entire study time frame. For example, sending a message action only occurred when an individual initiated a message send in MyChart Bedside. Passive actions occurred automatically, were non-exclusive, and were unreliable. For example, every five minutes the tablet refreshed telemetry data through no action of the patient. As a result, the research team sought to identify all active actions and associated them with one of the 10 functions offered in MyChart Bedside.

6.3.6 Survey data cleaning

Occasionally, respondents to the paper survey chose multiple responses to single response question. Such responder error was treated as non-response.

6.3.7 Merging billing data with encounters

Patient encounters and billing data may not have merged uniquely, as a single hospital charge record often incorporated multiple hospital encounters. Approximately 4.6% of the encounter dataset had billing data associated with multiple encounters. Additionally, because of the processing choice to merge close and overlapping encounters, multiple charges could have been associated with a single encounter. While the billing data was neither reported nor associated with a primary or secondary outcome, the study team thought it important to disclose its existence as part of this protocol document, as subsequent exploratory data analysis in other papers may refer to this data.

6.3.8 Additional exclusions

Several cases were identified post-hoc that created additional exclusions:

1. A negligible number of patients were enrolled in the study and in a subsequent visit were admitted as prisoners. In these cases, the enrolled participants were dropped from the analysis.

2. Study participants were dropped from the data if they withdrew from the study and were enrolled for less than three days. The study team determined that in these cases, the patient effectively indicated the intent to not be part of the study, despite originally agreeing to participate in the research.
3. Study participants with a length of stay less than three days were also dropped from the analysis. In prior work, it was determined that provisioning of tablets was not consistent for patients with length of stay less than three days.²⁰
4. Study participants with no MyChart Bedside use in their enrollment admission were excluded from analysis. These cases may have occurred because an individual was enrolled into the study using a paper survey, but then never received their tablet.

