### 1.4 Assumptions and testing

#### 1.4.1 Analysis populations

Estimates of the intervention effects were calculated on two analytic populations. The main analytic population of the study used an *intention-to-treat (ITT)* approach. Using this paradigm, participants were analyzed on the basis of the study group to which they were randomized, regardless of their eventual receipt of that intervention.

The effects of the intervention were additionally evaluated on a *per-protocol* population, composed exclusively by those participants who were administered their randomized intervention. The analysis of the data from the per-protocol population was weighted by the inverse of their probability to receive the intervention to which they were originally randomized, computed on the basis of the following demographic and clinical characteristics: sex, race, age at time of enrollment, Charlson Comorbidity Index, length of stay.

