#### **1.4.5 Defining MyChart Bedside use sessions**

A new MyChart Bedside use session was identified in the log files in two ways: (1) a “identify user with lock” action; or (2) any user action that occurred more than 15 minutes after the previous action. Some session periods contained no active tasks as defined in Section 6.3.5 in the Final Protocol. These inactive sessions were dropped from analyses. The “identify user with lock” action that marked the beginning of a session sometimes occurred multiple times sequentially without any other actions occurring. Retaining these recurring actions would create sessions with only a login action. To eliminate this problem, sequential “identify user with lock” actions were dropped.

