#### 1.5.1 Outcome 1 – Number of MyChart Bedside sessions within the enrollment admission was dependent on treatment

*Dependent variable specification:* The count of MyChart Bedside sessions for the admission associated with study enrollment.

- Enrollment admission was defined as the admission when the patient was enrolled in the study.

*Statistical model:* Negative binomial model with non-interacted and interacted study arms as binomial predictors.

---

ii Preliminary analysis of adoption rates for the outpatient portal revealed a rapid decrease in the numbers following the first few months, which motivated us to set the value for the cutoff date at 90 days in order to more conservatively attribute portal use to an individual's participation in the study.

*Covariates:* No covariates were added to this analysis.

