### 1.5.2 Outcome 2 – Comprehensive use was dependent on treatment

*Dependent variable specification:* A binary variable identifying participants that used all available functions based on their Tech arm assignment (1 = comprehensive functions user; 0 = not a comprehensive functions user).

- The definition of “comprehensiveness” was tested in two different ways:
  - **Definition 1: Based on use of all available functions:** Users were considered comprehensive functions users when they reached a threshold number of functions used based on their Tech Arm. For Lite-Tech users, this threshold was three selectable functions available—Bedside Tutorial, Dining on Demand, and To Learn. For Full-Tech users, this threshold was eight of the 10 functions available, including the three functions available to Lite-Tech users.
  - **Definition 2: Based on use of the functions available to all users:** Users were considered comprehensive functions users when they used the three functions that were available to all users.

*Statistical model:* Logistic regression model with non-interacted and interacted study arms as binomial predictors.

*Covariates:* No covariates were added to this analysis.

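### Protocol 6.3.8 item 4 drops non-users post hoc, which removes the zero value of primary H1 Outcome 1; its stated reason supports only an exclusion for tablets never provisioned

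*Protocol*

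**What the plan says.** Protocol 6.3.8 introduces its four exclusions as found post hoc. Item 4 reads: "Study participants with no MyChart Bedside use in their enrollment admission were excluded from analysis". It adds that such cases may have arisen when someone enrolled on paper and then never got a tablet.

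Protocol 2.2 places H1, higher use of MyChart Bedside, among the primary hypotheses. SAP 1.5.1 defines its first outcome as "The count of MyChart Bedside sessions for the admission associated with study enrollment". SAP 1.5.2 defines the second as "A binary variable identifying participants that used all available functions based on their Tech arm assignment", scored 0 for everyone else.

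Protocol 5.1.1 says "Only patients who were provisioned with MyChart Bedside were included in the study". SAP 1.4.2 puts the length of tablet provisioning, in days, into all models as an offset.

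Item 4 does not define *use*. Protocol 6.3.5 separates active from passive log actions. SAP 1.4.5 says of sessions without an active task: "These inactive sessions were dropped from analyses".

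**The concern.** The exclusion and H1 Outcome 1 look at the same behaviour in the same admission, so item 4 deletes one end of the outcome's range after allocation. H1 asks whether the interventions raise use, and turning a non-user into a user is one way to do that. Once non-users are gone, that part of the effect is invisible. If their share differs between arms, the comparison among those left is also shifted.

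Two features of the interventions could make the share differ. High-Touch patients were encouraged to follow the training on their own tablet (Protocol 3.1.2), which may itself create log activity. Lite-Tech offered 3 selectable functions against 10 in Full-Tech (Protocol 3.1.1), so Lite-Tech patients had fewer ways to register an active action. These are mechanisms, not observed counts.

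The SAP describes no analysis that keeps the zeros.

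**Working it through.** **What a recorded zero can mean.**
- *Tablet never provisioned.* Protocol 5.1.1 puts this person outside the study, so exclusion can be defended as eligibility. Such a person also has no provision time for the offset.
- *Tablet provisioned, Bedside not used.* This is a true 0 on Outcomes 1 and 2. If *use* means sessions as SAP 1.4.5 counts them, the group includes patients whose only sessions had no active task.

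Item 4 treats the two alike.

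**Size.** The readable text gives no count for item 4, so there is no plan figure to reproduce. Table 2 is internally consistent: 624 + 1,523 + 277 + 468 = 2,892, and 901 + 1,991 = 2,892. The text does not say whether these counts precede or follow item 4.

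Let zL and zH be the shares of provisioned tablet-days held by non-users in the Low and High arms. Non-users add tablet-days but no sessions, so for the crude session rate:

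ratio among users = ratio with zeros kept × (1 − zL)/(1 − zH)

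The relation is exact for crude rates and approximate for the negative binomial fit. To scale it for the Touch contrast, take SE(log ratio) = CV × √(1/nH + 1/nL). With an assumed coefficient of variation (CV) of 1.0 for the session rate among users, and clustering ignored, √(1/901 + 1/1,991) = 0.0402.

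| Assumed zL vs zH | Factor | Shift in SE, abs(ln factor)/0.0402 |
|---|---|---|
| 5% vs 5% | 0.95/0.95 = 1.000 | 0 |
| 1% vs 0% | 0.99/1.00 = 0.990 | 0.25 downward |
| 2% vs 1% | 0.98/0.99 = 0.990 | 0.25 downward |
| 5% vs 2% | 0.95/0.98 = 0.969 | 0.77 downward |
| 2% vs 5% | 0.98/0.95 = 1.032 | 0.77 upward |

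With zH = 0, a shift of one SE needs zL = 1 − exp(−0.0402) = 3.9 points. The randomised Touch split is not known, because Table 2 is realised and may reflect the reassignment in Protocol 4.3. Two other splits give:
- 50:50 with CV 0.8: SE = 0.8 × 0.0372 = 0.0298, gap 2.9 points.
- 75:25 with CV 1.5: SE = 1.5 × 0.0429 = 0.0644, gap 6.2 points.

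For the Tech contrast at the realised split, √(1/2,147 + 1/745) = 0.0425. The 1% vs 0% and 5% vs 2% cases then shift the estimate by 0.0101/0.0425 = 0.24 SE and 0.0311/0.0425 = 0.73 SE.

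**Outcome 2.** Assume 20% of users are comprehensive in both arms, so the users-only odds ratio is 1.00. With zeros kept, p = 0.20 × (1 − z):
- 1% vs 0%: 0.198 vs 0.200, odds ratio 1.013.
- 5% vs 2%: 0.190 vs 0.196, odds ratio 1.039.

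**A second view, with zeros generated by the count model.** Take P(0) = (1 + aμ)^(−1/a) and a true mean ratio of 1.20. With Low mean μ = 10 and dispersion a = 0.5, zeros are 2.8% vs 2.0%, and the ratio among users is 1.20 × 0.972/0.980 = 1.19. With μ = 2 and a = 1, zeros are 33% vs 29%, and the ratio is 1.20 × 0.667/0.706 = 1.13. The second case needs a third of Low-arm participants to be non-users, which fits poorly with how patients were enrolled.

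**The case against.** **Few zeros.** Participants had accepted a tablet (Protocol 5.1.1). Electronic consent was reached inside Bedside (5.2.1), as was the default Admission survey (3.8.2). Stays under three days were already dropped (6.3.8 item 3). If opening the consent tab counts as use, electronic enrollees were users before any training, and item 4 reaches mainly the paper enrollees it names. This stands as a reason to expect a small effect. It does not settle the matter, because *use* is undefined and neither consent nor the survey is among the functions listed in Protocol 3.1.1.

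**Intention to treat.** A reader might infer that item 4 as a whole breaches SAP 1.4.1, where "participants were analyzed on the basis of the study group to which they were randomized, regardless of their eventual receipt of that intervention". The documents do not support a charge that broad. Leaving out people who never had a tablet can rest on Protocol 5.1.1, and the fix below does the same. The dispute is about the proxy: log use in place of the provisioning record.

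**Linkage.** A reader might also infer that many zeros are failed record matches, since "There was no existing unique key to match MyChart Bedside use to hospital encounter data" and, for some patients, "data was written to the log files with the temporary MRN". But Protocol 6.3.1 calls such cases rare and recodes them to a primary number. Protocol 6.3.4 matches by timestamp, with about 1.5% of raw log actions falling outside an encounter. A false zero needs all of a participant's actions to be lost. This is a minor residual source.

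**Model fit.** SAP 1.4.4 reports that a zero-truncated model fitted best, by a margin it viewed as marginal. That is consistent with zeros having been removed, but it does not show how many.

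**Conclusion.** The point holds as a matter of definition. A post hoc rule selects the H1 analysis set on a primary outcome, and its stated reason covers only some of those it removes.

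What follows for the estimate is conditional. If non-use is rarer in the High arms, a positive effect is biased toward the null. If it is equal, the ratio is unchanged. If it is commoner, the ratio is inflated. The documents do not support a claim that H1 is known to be biased in one direction or by a material amount. For gaps of 1 to 3 points, the illustration gives 0.25 to 0.77 SE on the Touch session ratio and about 1% to 4% on the Outcome 2 odds ratio. The non-use shares, the CV and the 20% rate are all assumed, and hospital clustering is ignored.

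Figure 1 may hold the counts. It is not readable here, so their absence from the text is not a fault of the plan. The rule should still be changed: it bears on a primary outcome and is cheap to correct.

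**What to change.** 1. Replace item 4 with an exclusion for documented non-provisioning, justified by Protocol 5.1.1 and applied identically in all randomised arms. Use the provisioning data behind the SAP 1.4.2 offset. Protocol 6.2 names no provisioning table, so first confirm that these data, with the daily list in Protocol 5.2, can establish receipt.
2. State whether *use* means any log action or a session with an active task.
3. Keep provisioned non-users in H1 Outcomes 1 and 2 as 0 sessions and not comprehensive, with their own provision length as offset. Show the users-only result as a sensitivity analysis.
4. Where receipt cannot be settled, show H1 with and without those records.
5. Label H1 Outcome 3 (SAP 1.5.3) as users only, since its proportion is undefined when total actions are zero.
6. Report zero-use counts by randomised arm, if Figure 1 does not already do so.

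The cost is a check of the zero-use records and a re-run on existing data. Mean use will fall slightly, and a few records may stay undetermined.
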